AUC area under the plasma/serum concentration versus time curve

AUC_{0-t} partial area under the concentration versus time curve from time "0" to time "t"

AUC_{last} area under the concentration versus time curve from time zero to the last quantifiable

concentration

AUC_{tau} area under the concentration versus time curve over the dosing interval AUC_{inf} area under the concentration versus time curve from time zero to infinity

C_{last} last observed quantifiable concentration of the drug

C_{max} maximum observed concentration of drug

C_t concentration at time t

C_{tau} observed drug concentration at the end of the dosing interval

C_{trough} concentration at the end of the dosing interval

CL/F apparent oral clearance after administration of the drug:

 $CL/F = Dose/AUC_{inf}$, where "Dose" is the dose of the drug

 T_{last} time (observed time point) of C_{last} T_{max} time (observed time point) of C_{max}

 $t_{1/2}$ estimate of the terminal elimination half-life of the drug, calculated by dividing the natural log of

2 by the terminal elimination rate constant (λ_z)

 V_z/F apparent volume of distribution of the drug

 λ_z terminal elimination rate constant, estimated by linear regression of the terminal elimination

phase of the concentration of drug versus time curve

1. INTRODUCTION

This statistical analysis plan (SAP) describes the statistical analysis methods and data presentations to be used in tables, figures, and listings (TFLs) in the clinical study report (CSR) for study GS-US-544-5905-03 (Master Protocol GS-US-544-5905, Substudy 03). This SAP is based on the study GS-US-544-5905 master protocol Amendment 2 dated 24 February 2023, substudy GS-US-544-5905-03 protocol Amendment 1 dated 18 August 2023, and the electronic case report form (eCRF) for study GS-US-544-5905-03. The SAP will be finalized before study GS-US-544-5905-03 database finalization. Any changes made after the finalization of the SAP will be documented in the study GS-US-544-5905-03 CSR.

1.1. Study Objectives

The primary objective of this substudy is to evaluate the short-term antiviral activity of GS-6212 with respect to the change from baseline in plasma HIV-1 RNA (log₁₀ copies/mL) on Day 11 in people with HIV-1 (PWH) who are antiretroviral (ARV) treatment naive or treatment experienced but naive to the integrase strand-transfer inhibitor (INSTI) class, and have not received any antiretroviral therapy (ART) within 12 weeks of screening including medications received for pre-exposure prophylaxis (PrEP) or postexposure prophylaxis (PEP).

The secondary objectives of this substudy are as follows:

- To evaluate the short-term antiviral activity of GS-6212 in reducing plasma HIV-1 RNA (log₁₀ copies/mL)
- To investigate the safety and tolerability of GS-6212 by dose cohort
- To characterize the plasma pharmacokinetics (PK) of GS-6212
- To characterize the PK/pharmacodynamic (PD) relationship between the exposure of GS-6212 and the viral dynamics of HIV-1
- To determine the number and percentage of participants who achieve HIV-1 RNA < 50 copies/mL of the HIV-1 RNA assay by Day 11 at each dose level
- To examine the emergence of resistance to the INSTI drug class

1.2. Study Design

This is an open-label Phase 1b, multiple dose, multicohort, substudy to an umbrella study designed to evaluate safety, PK, and antiviral activity of GS-6212 given as monotherapy in PWH who are either treatment-naive or treatment experienced but naive to the study drug class, and have not received any ART within 12 weeks of screening, including medications received for preexposure prophylaxis (PrEP) or postexposure prophylaxis (PEP). Any current or prior receipt of long-acting parenteral ARVs including: monoclonal antibodies (mAbs) targeting HIV-1, injectable cabotegravir, or injectable rilpivirine, is exclusionary.

This umbrella study will consist of a master protocol describing information relevant to all substudies; and each novel compound will have its own substudy. GS-US-544-5905-03 will be the third substudy with GS-6212 as the compound. This flexible clinical study design allows for opening new substudies as new agents become available and closing substudies with study drugs that demonstrate minimal clinical activity and/or unacceptable toxicity.

After screening and meeting all eligibility criteria, study drug dosing will be initiated on Day 1 in the clinic for each participant. Participants will be required to return to the clinic for visits on Days 2, 3, 4, 7, 8, 9, 10, and 11 (primary endpoint assessment). Doses of GS-6212 will be administered orally at the clinic under observation by site staff on clinic visit days/times and at home by the participant on nonclinic visit days/times at approximately the same time each day. In cohorts where GS-6212 is administered more than once daily, in-clinic observation of dosing will be conducted for the morning dose only. Participants will record at-home dosing details in a dosing log.

After assessments on Day 11 or upon early termination (ET), participants will initiate a regimen of Biktarvy® (bictegravir/emtricitabine/tenofovir alafenamide; BVY) provided by the sponsor or an alternative standard-of-care (SOC) ART regimen selected by the investigator. If participants are switching to BVY, a sufficient supply will be given to provide coverage for the remainder of the study. Participants will be required to return to the clinic for a follow-up visit on Day 25.

Overnight fasting (\geq 6 hours prior to dosing) is required for laboratory and/or PK analyses on Days 1 and 11 (see Section 5.3). On all other days (Days 2 through 10), the AM doses should be taken on an empty stomach.

Following study completion, the participant's care will be transferred to a primary health care provider who will determine the participant's HIV long-term treatment plan.

This substudy will enroll up to 5 cohorts with at least 6 participants in each cohort. Participants will be enrolled in Cohort 1 initially and then dosing in subsequent cohorts will proceed as appropriate after safety review team (SRT) review of emerging data from Cohort 1 and available data from the Phase 1a SAD/MAD Study GS-US-469-6401.

The dose level and dosing regimen for study drug in each cohort will be selected based on a review of available PK, cumulative safety, and HIV-1 RNA data through the primary endpoint (Day 11) for this substudy, and/or relevant and available safety and PK data from the ongoing Phase 1a first-in-human (FIH) study for GS-6212.

Assessments will be conducted per the schedule of assessment table (see Schedule of Assessments, Appendix 1).

1.3. Sample Size and Power

A sample size of 6 to 8 participants in each dose cohort will provide 83% to 94% power to detect a treatment difference of $1.0 \log_{10} \text{copies/mL}$ in change from baseline in HIV-1 RNA on Day 11 between at least one of the study drug dose groups and the historical placebo group (N = 21). In this power analysis, it is assumed that a standard deviation (SD) for the change from baseline in

HIV-1 RNA on Day 11 is 0.662 log₁₀ copies/mL for each study drug dose group and 0.359 log₁₀ copies/mL for the placebo group, and a 2-sided t-test is conducted at an alpha level of 0.05. Standard deviations were estimated from historical Phase 1b studies conducted by the sponsor (GS-US-120-0104, GS-US-141-1219, and GS-US-200-4072). The maximum SD from treatment groups was used for the study drug dose group and SD from the pooled placebo group was used for the placebo group.

2. TYPE OF PLANNED ANALYSIS

2.1. Interim Analysis

Before the final analysis, interim analyses may be conducted and the analyses may be submitted to regulatory agencies to seek guidance for the overall clinical development program of GS-6212.

2.2. Dose Escalation Analysis

A safety review team (SRT) will review the data from this substudy after all participants from Cohort 1 complete their Day 11 visit. The SRT review will include cumulative safety and HIV-1 RNA data through the primary endpoint (Day 11) and available PK data from Cohort 1 of this substudy; and/or relevant and available safety and PK data from the Phase 1a FIH study for GS-6212 (as appropriate). This initial SRT review will facilitate decision-making for dose level, dosing regimen (including whether GS-6212 study drug will be taken in a fasted state, or with a low-fat or high-fat meal) and timing of dosing for Cohorts 2 to 5. Following SRT review of Cohort 1, no additional cohorts were required. Cohorts 2-5 were not enrolled.

2.3. Final Analysis

The final analysis will be performed after all participants have completed the study, outstanding data queries have been resolved or adjudicated as unresolvable, and the data have been cleaned and finalized. The analysis of the primary endpoint (change from baseline in HIV-1 RNA [log₁₀ copies/mL] on Day 11) will be conducted at the time of the final analysis and will be tested at the 0.05 significance level (2-sided test).

3. GENERAL CONSIDERATIONS FOR DATA ANALYSES

Analysis results will be presented using descriptive statistics. For categorical variables, the number and percentage of participants in each category will be presented; for continuous variables, the number of participants (n), mean, SD or standard error (SE), median, first quartile (Q1), third quartile (Q3), minimum (Min), and maximum (Max) will be presented.

All statistical tests will be 2-sided and performed at the 5% significance level unless otherwise specified.

By-participant listings will be presented for all participants in the All Enrolled Analysis Set and will be sorted by participant identification (ID) number, visit date, and time (if applicable), unless otherwise specified. Data collected on log forms, such as AEs, will be presented in chronological order within participants. The treatment group to which participants were initially assigned will be used in the listings. Age, sex at birth, race, and ethnicity will be included in the listings, as space permits.

3.1. Analysis Sets

Analysis sets define the participants to be included in an analysis. Analysis sets and their definitions are provided in this section. The analysis set will be identified and included as a subtitle of each table, figure, and listing.

For each analysis set, the number and percentage of participants eligible for inclusion as well as the number and percentage of participants who were excluded and the reasons for their exclusion will be summarized in the disposition table as detailed in Section 4. A listing of reasons for exclusion from analysis sets will be provided by participant.

3.1.1. All Enrolled Analysis Set

All Enrolled Analysis Set includes all participants who received a study participant ID number in the study after screening.

All Enrolled Analysis Set is the primary analysis set for by-participant listings.

3.1.2. Full Analysis Set

The Full Analysis Set (FAS) includes all participants who were enrolled and received at least one dose of GS-6212 study drug in this substudy. Participants will be grouped according to the GS-6212 cohort assigned at enrollment.

Participants who were randomized and assigned to receive placebo from 3 historical Gilead Phase 1b studies (GS-US-120-0104, GS-US-141-1219, and GS-US-200-4072) will be used as a historical control through Study Day 11 for only the HIV-1 RNA endpoints.

The Full Analysis Set will be the primary analysis set for efficacy analyses.

3.1.3. Safety Analysis Set

The Safety Analysis Set includes all participants who took at least 1 dose of GS-6212 in this study. Participants who received treatment other than that assigned at enrollment will be analyzed according to the treatment that they received.

All data collected on/after first dose date of GS-6212 during the study will be included in the safety summaries.

The Safety Analysis Set is the primary analysis set for safety analyses.

3.1.4. Pharmacokinetic Analysis Set

The PK Analysis Set includes all participants who were enrolled in the study, received any dose of GS-6212 in this study, and have at least 1 nonmissing post baseline concentration value for GS-6212.

The PK Analysis Set is the primary analysis set for all PK analyses.

3.2. Participant Grouping

For analyses based on the FAS, participants will be grouped according to the GS-6212 cohort to which they were enrolled. Data from participants who were randomized and assigned to receive placebo from 3 historical Gilead Phase 1b studies (GS-US-120-0104, GS-US-141-1219, and GS-US-200-4072) will be pooled to form a historical placebo group for HIV-1 RNA endpoints through Day 11. For all other analyses, participants will be grouped according to the actual GS-6212 treatment received in this study.

3.3. Strata and Covariates

No covariates will be included in efficacy analyses.

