6. EFFICACY ANALYSES

6.1. Primary Efficacy Endpoint

The primary efficacy endpoint is the change from baseline in plasma HIV-1 RNA (log₁₀ copies/mL) on Day 11.

Historical HIV-1 RNA data for placebo participants from 3 sponsor Phase 1b studies (GS-US-120-0104, GS-US-141-1219, and GS-US-200-4072) will be combined to form a single placebo group for the purpose of HIV-1 RNA analysis through Study Day 11. For Study GS-US-200-4072, HIV-1 RNA (log₁₀ copies/mL) collected on Day 10 will be used for "Day 11" since HIV-1 RNA was not collected on Day 11 for this study. GS-6212 cohort will be compared to the pooled placebo group with respect to the primary efficacy endpoint, the change from baseline in plasma HIV-1 RNA (log₁₀ copies/mL) on Day 11, using the 2-sided t-test conducted at an alpha level of 0.05. The analysis will be conducted using the FAS.

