Appendix 2. Details for Statistical Programming

For continuous HIV-1 RNA endpoints change from baseline on Day 11, and maximum change from Day 2 to Day 11, pairwise comparisons between GS-6212 cohort and historical placebo group will be performed and p-values will be presented.

The following SAS code will be used to generate p-values:

```
**Assign treatment groups for testing**;
data trtgrp;
set trtgrp;
   if dose ='100 mg' and meal='Fasted' then trt=1;
   else if treatment='Placebo' then trt2;
run;

ods output estimates=estimate;
proc mixed data = trtgrp;
class trt;
model chg = trt / ddfm=kr;

/*least squares means*/
lsmeans trt / diff e;

/* p-values */
estimate 'Cohort 1 vs Placebo' trt 1 -1 / cl alpha=0.05;
run;
```

GS-US-544-5905-03_SAP ELECTRONIC SIGNATURES

Signed by	Meaning of Signature	Server Date (dd-MMM- yyyy hh:mm:ss)
PPD	Biostatistics eSigned	28-Aug-2024 03:56:43
PPD	Project Team Leader eSigned	28-Aug-2024 16:23:03
PPD	Clinical Pharmacology eSigned	28-Aug-2024 16:42:19

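### The primary comparison with historical placebo has no baseline-adjusted sensitivity analysis, so any dependence of the result on baseline HIV-1 RNA goes unexamined

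*SAP*

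**What the plan says.** Section 6.1 defines the endpoint: "The primary efficacy endpoint is the change from baseline in plasma HIV-1 RNA" on Day 11. The comparator is not a concurrent arm. Under 3.2, placebo data from three earlier sponsor studies "will be pooled to form a historical placebo group for HIV-1 RNA endpoints through Day 11". The GS-6212 cohort is compared with that group "using the 2-sided t-test conducted at an alpha level of 0.05".

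Section 3.3 is categorical: "No covariates will be included in efficacy analyses". Appendix 2 agrees with it; the programmed model is "model chg = trt / ddfm=kr", with no baseline term.

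Section 6.4 limits its sensitivity analyses to participants who were correctly dosed and completed study drug, and reuses the primary method. Section 3.7 allows transformation or nonparametric methods, but not adjustment. Section 6.3 does plan descriptive summaries of baseline HIV-1 RNA for both the cohort and the historical placebo group.

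**The concern.** Without concurrent randomisation, the two groups can differ systematically in baseline HIV-1 RNA. Taking change from baseline removes that difference only if change does not itself depend on the starting value. There are at least two routes by which it could:

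- regression to the mean;
- a floor, because 3.7 sets values below the quantitation limit to one unit under that limit, so the largest recordable fall is capped by the starting value. This matters only for low baselines or deep responses.

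If such a dependence exists and the groups start at different levels, the estimated difference is shifted. The tables in 6.3 would show the gap, but no planned analysis would show whether the result depends on it. Any adjustment would then be chosen after the gap had been seen. Section 2.2 records that Cohorts 2 to 5 were not enrolled, so no dose-response pattern is available to support this one comparison.

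**Working it through.** **Inputs from the SAP (1.3):** n = 6 to 8 on drug; 21 historical placebo; SD of change 0.662 (drug) and 0.359 (placebo); effect 1.0 log10; 2-sided alpha 0.05.

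**Assumed, because the SAP does not give them:** baseline gap D = 0.5 log10; slope of change on baseline 0.2 to 0.4 in absolute size (0.1 to 0.5 for the error rates); baseline SD 0.5 to 0.7.

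**1. The plan's own figure.** Section 1.3 states: "A sample size of 6 to 8 participants in each dose cohort will provide 83% to 94% power". With unequal variances, SE = √(0.662²/n + 0.359²/21).
- n = 6: √(0.0730 + 0.0061) = 0.281; Welch df 5.87; noncentrality 1.0/0.281 = 3.55; power 83.6%.
- n = 8: √(0.0548 + 0.0061) = 0.247; df 8.62; noncentrality 4.05; power 94.6%.

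The stated figures therefore reproduce with an unequal-variance t-test. An equal-variance test gives 99.7% to 99.9% and does not match. The 95% CI half-widths are 0.69 (n = 6) and 0.56 (n = 8).

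**2. Bias of the unadjusted estimate if change depends on baseline.** Bias = slope × D.
- 0.2 × 0.5 = 0.10; 0.4 × 0.5 = 0.20.
- In SE units: 0.10/0.281 = 0.36 up to 0.20/0.247 = 0.81.
- As a share of the CI half-width: 0.10/0.69 = 14% up to 0.20/0.56 = 36%.

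The sign follows the gap. If higher baselines go with larger falls, a cohort that starts higher than placebo looks better than it should, and one that starts lower looks worse.

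**3. Effect on the error rate (simulated Welch test, D = 0.5).**

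| Slope | Type I error, n = 6 | Type I error, n = 8 |
|---|---|---|
| no bias | 5.5% | 5.1% |
| 0.1 | 5.7% | about 5.7% |
| 0.2 | 6.4% | 6.8% |
| 0.3 | 8.0% | 8.7% |
| 0.5 | 12.5% | 15.2% |

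**4. Bias of the adjusted estimate in the opposite case.** Suppose there is no drug effect, the populations truly differ by D, and the slope arises only from noise in the baseline measurement, so each group regresses to its own mean. Expected change is zero in both groups and the unadjusted bias is 0. Adjustment subtracts slope × D that was never there, giving a bias of 0.2 × 0.5 = 0.10 to 0.4 × 0.5 = 0.20. This is the same size as in step 2.

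**5. Where the slope would come from.** Assuming similar baseline spread in both groups, information on a common slope is proportional to (n − 1)/SD². Placebo: 20/0.359² = 155.2. Drug: 5/0.662² = 11.4 (n = 6) or 7/0.662² = 16.0 (n = 8). The placebo share is 155.2/166.6 = 93% or 155.2/171.2 = 91%.

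**6. Precision.** The drug arm supplies 0.0730/0.0791 = 92% (n = 6) or 0.0548/0.0609 = 90% (n = 8) of the variance of the difference. There, correlation = slope × baseline SD / 0.662, from 0.2 × 0.5/0.662 = 0.15 to 0.4 × 0.7/0.662 = 0.42, so r² is 2% to 18%. Approximate power with baseline added is 80% (n = 6) and 94% (n = 8) at zero correlation, and 84% and 96% at correlation 0.3. Adjustment costs little and gains little.

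**The case against.** The strongest defence is that the choice is explicit and consistent. Sections 3.3 and 6.1 and Appendix 2 agree on having no covariates, 1.3 powers an unadjusted test, and 3.5 calls this a proof-of-concept study. Baseline is already subtracted within each participant, and 6.3 will show both groups' baselines. Adjustment can also create bias (step 4), and its slope would come mainly from placebo recipients, who may not show how response to drug varies with starting level (step 5). All of this stands. It rules out calling the omission an error and argues against replacing the primary model. It does not explain why a supportive analysis is excluded as well.

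Three stronger readings are tempting, and the SAP does not support them:

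- A reader might infer that a baseline gap enters the primary estimate in full. It would do so only with a slope of 1; for a change score the quantity is slope × gap.
- A reader might count chance imbalance as bias. With baseline SD 0.5 to 0.7, the SE of the baseline difference is 0.21 to 0.32 log10 (SD × √(1/n + 1/21)), but its effect on change is sampling variation already inside the SE. Only a systematic gap between study populations counts.
- A reader might expect adjustment to repair the comparison and tighten the interval. Step 4 shows it can bias, step 6 shows the precision gain may be nil, and it leaves other differences between the studies untouched.

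**Conclusion.** The point holds as a gap in the sensitivity analyses. The comparison is non-randomised, baseline HIV-1 RNA is in hand for every participant whose change is computed, and no planned analysis tests whether the result depends on it. Under the assumed gap of 0.5 log10 and slope of 0.2 to 0.4, the unexamined shift is 0.10 to 0.20 log10, direction unknown. That is modest against a true effect of 1.0 and unlikely to reverse the conclusion. It matters more for the size of the estimate, its interval, or a smaller true effect. All of these magnitudes rest on assumed values. The SAP does not establish that a gap exists, nor which of the two estimates would be the biased one. That uncertainty is the reason to report both.

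**What to change.** - **6.1:** keep the unadjusted comparison as primary, stated as an unequual-variance (Welch) t-test, which is the form that reproduces the power in 1.3. The Appendix 2 code has no group-specific variance. That is a separate matter, but both analyses should rest on the same variance assumption.
- **3.3:** amend to allow baseline log10 HIV-1 RNA as a covariate in sensitivity analyses of the continuous HIV-1 RNA endpoints.
- **6.4 and Appendix 2:** add that analysis, for example `model chg = base trt / ddfm=satterthwaite; repeated / group=trt;`, and report it beside the primary estimate and the baseline means already planned in 6.3.
- **Status:** under 2.2 the review of Cohort 1, which was to include HIV-1 RNA through Day 11, has already taken place. The addition should be dated and, as section 1 requires for changes after SAP finalisation, documented in the CSR.

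The cost is one model term, one degree of freedom and one row of output, with no new data. The drawbacks are an imprecise slope drawn mostly from placebo participants, and possible bias in the adjusted estimate if the study populations truly differ. For both reasons the analysis should be labelled supportive.

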3.4. Examination of Participant Subgroups

There are no prespecified participant subgroups for efficacy or safety analyses.

3.5. Multiple Comparisons

Adjustments for multiplicity will not be made in this proof-of-concept study.

3.6. Missing Data and Outliers

3.6.1. Missing Data

In general, missing data will not be imputed unless methods for handling missing data are specified. Exceptions are presented in this document.

The handling of missing or incomplete dates for AE onset is described in Section 7.1.6.2, and for prior and concomitant medications in Section 7.4.

3.6.2. Outliers

Outliers of non-PK will be identified during the data management and data analysis process, but no sensitivity analyses will be conducted. All data will be included in the data analysis.

Outliers of PK data may be identified during review of data by the PK scientist, and if necessary, appropriate sensitivity analyses may be conducted.

